3.3 Levels of confidence and p values

Statistical tests and confidence intervals will be two-sided. 95% confidence intervals will be presented wherever possible. The statistical significance level set will be at the 5% level.

3.4 Unadjusted and adjusted analyses

The urinary variables will be used with adjustment for creatinine levels to account for urine dilution. If outcomes are not normally-distributed and the analyses require the normality assumption, then outcomes will be log-transformed (natural logarithm).

3.5 Multiple testing

Multiple testing will be accounted for, using the Benjamini-Hochberg (false discovery rate, FDR) method considering all the regression parameters of the primary and post-hoc analyses. Q-value <0.05 indicates statistical significance of an association after controlling the false discovery rate at 5%.

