2.2 Study Objectives

Primary Objectives:

1. To investigate the effect of skin temperature gradient on the diurnal variation of adipokines and stress hormones in the two settings (urban and rural). (Null hypothesis: There is no association of skin temperature gradient with adipokine secretion.)
2. To investigate the circadian patterns of adipokines (leptin, adiponectin, and ghrelin hormones), cortisol, and melatonin in healthy individuals residing in two different climatological environments: urban and higher in latitude rural. (Null hypothesis: There is no difference in the circadian rhythm of the metabolic hormones between participants at the urban or rural environments.)

Secondary Objective:

1. To examine metabolite differences in the metabolomics-based profiles of healthy individuals with non-obese body weight in two study settings with distinctly different climatological characteristics.

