2.9 Sample Size

To estimate the sample size, the sample size program by the MGH Biostatistics Center was used (Schoenfeld, 2010). We used the paired t test study design for calculating the power of this test, assuming that each subject has a pair of values (one for the urban setting and one for the rural mountainous setting). The variable used for the estimation of the sample size was one of the adipokines (serum leptin), since it is one the primary outcomes for the trial and there is no available information for urinary adipokines.

The input parameters were: significance level, within patient standard deviation, power and minimal detectable difference in means. Based on the literature, the within subject standard deviation of plasma leptin was assumed to be 3.53 ppb for females and 0.01 ppb for males (Saad et al., 1998), and we hypothesized a minimal detectable difference in leptin levels between the urban and rural mountainous settings to be atleast 1.9 ppb, based on other intervention studies (Hibi et al., 2017; Fontes-Villalba et al., 2016). Assuming a power of 80% and a two-sided 5% significance level, the sample size for this two-treatment crossover study was estimated to be 57 subjects.

3 Statistical Analysis

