3.6 Missing Data and data below LOD

The underlying assumption for missing data in non-statistical terms include participants voluntarily or due to another factor (pregnancy, diabetes, hypertension) dropping out of the study or due to incomplete data in the diaries – questionnaires. Those kinds of data are considered censored and missing not at random and they will be denoted as ‘NA’ or as an “empty box” in any files with data.

For the urinary data below the limit of detection (LOD), imputation will be performed based on existing suggestions for handling non-detect urinary measured concentrations data (Helsel, 2005). For outcomes that contain $<20\%$ values below the detection limit, values $<\text{LOD}$ will be imputed as $\text{LOD}/2$ and for outcomes that contain $\geq 20\%$ values below detection, values $<\text{LOD}$ will be imputed with regression on order statistics (ROS). With the ROS method, non-detect data are replaced based on a probability plot of detects. Outcomes with $>70\%$ values below detection, will be used as binary variables in the primary, post-hoc and sensitivity analyses.

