3.9 Primary analysis of outcomes

3.9.1 Cosinor method

An exploratory analysis will be formed by plotting the data as a function of time for each sampling day. This will allow for visual observation of possible trends and for comparisons between sampling days. Residuals will also be plotted as a function of time that will provide valuable information on how to proceed for further analysis. A histogram will also be used to assess normality of the results.

Since prior information suggests a presence of rhythm with period of 24-hours, data will be stacked in classes in an attempt to reduce noise and reveal the rhythm's waveform. Class means will be used to test for a statistically significant time effect.

Once a rhythm has been validated, the single cosinor method will be used to model the rhythm by fitting a cosine curve, a procedure similar to the least square methods (Cornelissen, 2014). For each subject, a single-component cosinor will be created for each sampling day, and for each group, a population-mean cosinor will be created for each sampling day. These methods also involve certain assumptions that need to be satisfied hence; regression diagnostics will be implemented at this stage to assess the model's adequacy. Further statistical testing will be implemented to test the equality of parameters such as the MESORs, amplitudes and acrophases (Cornelissen, 2014) of the two groups in the two settings.

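### Primary tests share one Benjamini-Hochberg family with post-hoc analyses that the SAP never lists, so primary q-values can change with tests added after the data are seen

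*SAP*

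**What the plan says.** SAP section 3.5 defines the multiplicity family as "considering all the regression parameters of the primary and post-hoc analyses", corrected together by Benjamini-Hochberg. The decision rule follows: "Q-value <0.05 indicates statistical significance of an association after controlling the false discovery rate at 5"%.

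Post-hoc analyses are mentioned in one other place, the rule in section 3.6 for outcomes mostly below the detection limit, which "will be used as binary variables in the primary, post-hoc and sensitivity analyses". That sentence does not say what they are. Section 3.9 describes the primary analyses. Section 3.10 describes only the untargeted metabolomics, which it labels secondary. No section lists or counts a post-hoc analysis, and section 3.5 does not refer to a list held elsewhere.

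The primary hypotheses are in section 2.2. The first null is "There is no association of skin temperature gradient with adipokine secretion"; the second is "There is no difference in the circadian rhythm of the metabolic hormones between participants at the urban or rural environments". Section 2.8 names five primary hormones: leptin, adiponectin, ghrelin, melatonin and cortisol.

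**The concern.** A Benjamini-Hochberg q-value depends on every p-value in the family, through the family size and the ranks. If primary and post-hoc tests share one family and the post-hoc part is open, a primary result can gain or lose significance while the primary data stay the same. Post-hoc tests are commonly chosen once results are known, and nothing in the SAP prevents that here.

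There is a second problem, which would remain even with a fixed list. Control over the pooled set is an average over all rejections in it. It gives no 5% guarantee for the primary tests taken alone.

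At stake is which of the five primary hormones may be reported as significant.

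**Working it through.** **The plan's own figure.** Section 2.9 takes a within-subject SD of 3.53 ppb (the female value), a difference of 1.9 ppb, 80% power and two-sided 5%. The SD of the paired difference is √2 × 3.53 = 4.99, so the standardised effect is 1.9/4.99 = 0.381. The non-central t distribution then gives N = 57 with power 80.6%, which reproduces the stated 57. This figure does not bear on the family definition; it is used only for the power figures in step 4.

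**Assumed counts.** The SAP gives none. One possible primary count is 29:
- three gradient metrics × three adipokines = 9;
- for each of five hormones, one setting effect plus contrasts of MESOR, amplitude and acrophase, 5 × 4 = 20.

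The numbers of post-hoc tests are also assumed. Null p-values are uniform and clearly non-null ones are about 0.

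**1. Formula.** With p-values sorted, q(i) is the minimum over j ≥ i of p(j) × m/j, where m is the family size.

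**2. Null additions tighten the cut-off.** Take a lone small primary p of 0.0015 with all other p-values large. Among 29 tests q = 0.0015 × 29 = 0.0435. With five null post-hoc tests added, q = 0.0015 × 34 = 0.051, so significance is lost. In a family of five with p = 0.008, 0.03, 0.20, 0.45 and 0.70, the smallest q is 0.008 × 5 = 0.040. Two null additions make it 0.008 × 7 = 0.056.

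**3. Non-null additions loosen it.** With p = 0.03, 0.04, 0.20, 0.45 and 0.70, the smallest q is 0.04 × 5/2 = 0.100. Adding ten post-hoc tests at p = 0.0001 moves the 0.03 to rank 11 of 15, so q = 0.03 × 15/11 = 0.041. Significance is gained with no change in the primary data.

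**4. Power for one true leptin setting effect, all other tests null and independent (100,000 simulated trials, n = 57).**

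| Family | Power |
|---|---|
| Leptin test alone | 80% |
| 5 tests | 59% |
| 5 + 20 null post-hoc | 37% to 38% |
| 29 tests | 36% |
| 29 + 20 null post-hoc | 30% |
| 29 + 40 null post-hoc | 27% |

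**5. Chance of at least one false primary claim, all 29 primary nulls true (200,000 simulated trials).**
- 29 null tests only: 5%.
- With ten clearly non-null post-hoc tests: 34%. Check by hand: the cut-off at rank 11 is 0.05 × 11/39 = 0.0141, and 1 − (1 − 0.0141)^29 = 0.338.
- With those ten plus 20 null post-hoc tests: 24%.
- At correlation 0.5, the first two figures are about 4% and 20%.

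**6. Pooled false discovery rate in the 34% case.** For independent tests it is 0.05 × 29/39 = 3.7%. It is under 5%.

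**The case against.** The strongest reply is that section 3.5 adopts false discovery rate control, whereas the 34% is a family-wise measure. In that scenario the pooled false discovery rate is 3.7%. This stands: a reader might infer that the plan breaks its own 5% rate, and the documents do not support that. What remains is that pooled control does not protect the primary subset, and that the standard guarantee presumes a family not chosen from the results.

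Two other stronger readings are tempting and also fail:
- *The primary test count hinges on whether a rhythm is found.* Section 3.9.1 does say "Once a rhythm has been validated, the single cosinor method will be used to model the rhythm by fitting a cosine curve", and plans to "test the equality of parameters such as the MESORs, amplitudes and acrophases". But that condition governs the single cosinor. Section 3.9.3 commits without condition to non-linear mixed models of diurnal variation for all five hormones.
- *Intercepts and time terms enter the family and loosen it.* That follows only from reading every regression parameter literally. The decision rule speaks of the significance of an association, which may be meant to exclude them.

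It is also fair to say that every count is assumed, that ten near-zero post-hoc p-values is an extreme case, that the 0.0015 example was chosen to lie close to the cut-off (0.05/29 = 0.00172; 0.05/34 = 0.00147), and that hormones from the same participants are correlated. Correcting post-hoc tests is stricter than leaving them uncorrected, and section 2.1 calls the trial a pilot. The protocol, not at hand, may list the post-hoc analyses. These points limit the size. They do not remove the dependence: even with such a list, section 3.5 would still pool those tests with the primary ones.

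**Conclusion.** The point holds as a defect in a stated rule. Section 3.5 puts primary and unlisted post-hoc tests in one family, so tests added after the data are seen can change primary significance in either direction. The mechanism needs no assumed count; the sizes do. In the illustrations, five null additions take a primary q from 0.044 to 0.051, and ten near-certain additions take the chance of any false primary claim from 5% to about 34% under independence, or about 20% at correlation 0.5.

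No net direction is claimed, since null and non-null additions can offset each other. Nothing in the SAP shows an intention to add tests selectively; the wording merely permits it. The change should be made before analysis. Unadjusted estimates and confidence intervals are unaffected.

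**What to change.** Replace the family definition in section 3.5 with wording such as:

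> Benjamini-Hochberg at 5% is applied to a closed family of primary tests, listed before analysis. It contains only the coefficients that test the primary null hypotheses: for example, the rural-versus-urban effect for each of the five hormones, and any rhythm contrasts and gradient coefficients declared primary. Intercepts, time terms and adjustment covariates do not enter. A listed test that cannot be fitted counts as p = 1. Post-hoc analyses are corrected in a separate family and labelled exploratory.

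The sponsor chooses the list, consistent with both primary objectives, including the stress hormones named in the first. If gradient coefficients are listed, each needs a named model: section 3.9.3 specifies none, and section 3.9.2 defines magnitude and duration per gradient event.

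The cost is SAP wording and one list. There are three downsides:
- The 5% rate then holds per family and not over all results together.
- Little power is gained. A closed family of 20 tests gives about 40% for a lone leptin effect, against 37% to 38% for five tests pooled with 20 null post-hoc tests.
- Tests within the closed family still affect one another. If 15 of 20 are clearly non-null, the chance of a false claim among the other five is 1 − (1 − 0.05 × 16/20)^5, about 18.5%. A short primary list limits this.

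The gain is that the primary decision rule is fixed and no longer depends on post-hoc tests.

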3.6 Missing Data and data below LOD

The underlying assumption for missing data in non-statistical terms include participants voluntarily or due to another factor (pregnancy, diabetes, hypertension) dropping out of the study or due to incomplete data in the diaries – questionnaires. Those kinds of data are considered censored and missing not at random and they will be denoted as ‘NA’ or as an “empty box” in any files with data.

For the urinary data below the limit of detection (LOD), imputation will be performed based on existing suggestions for handling non-detect urinary measured concentrations data (Helsel, 2005). For outcomes that contain $<20\%$ values below the detection limit, values $<\text{LOD}$ will be imputed as $\text{LOD}/2$ and for outcomes that contain $\geq 20\%$ values below detection, values $<\text{LOD}$ will be imputed with regression on order statistics (ROS). With the ROS method, non-detect data are replaced based on a probability plot of detects. Outcomes with $>70\%$ values below detection, will be used as binary variables in the primary, post-hoc and sensitivity analyses.

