2.5 Intervention

Table 2 presents the details of the visits and the sample collection processes.

Table 2. Visits details and sample collection process in chronological order.

Visits/Sampling days	Description
Visit 1	
The researcher visits the participant one day before the sampling day 1 (6 days after being in the urban/rural setting) and the following procedures are performed:
 
 • Administrates the consent form and receives it signed by the participant • Administrates the Questionnaire A and Chronotype Questionnaire and receives them completed by the participant • Provides coded vials for urine sampling in plastic bag and explains • Provides activity diary and explanations • Places temperature sensors on the participant (after activating them on place) and explains • Provides the instructions for urine collection and temperature sensors

	
 • Arranges appointment for the sample collection two days later (ideally in the morning)
Sampling day 1	
The participant is wearing the sensors continuously from the previous day and collects the urine voids of the day (at least 4) except for the first morning void. The participant stores the urine vials in a plastic bag in the freezer/fridge. The participant notes in the activity diary, the activities of the day (including entrance/exit from buildings, sleep/wake cycle, physical activities and meals) and their corresponding time and the times that each urine void was collected.

Visit 2	
The participant collects the first morning void of the day after the sampling day and continues wearing the temperature sensors and noting in the diary.
 
The researcher visits the participant one day after the sampling day on the arranged time and the following procedures are performed:
 
 • Collection of the urine samples and sensors • Collection and check of the completed activity diary • Sensors data are transferred immediately on a laptop, to check that data were recorded • Arrangement for the next visit that will take place in the other setting (urban/rural) with at least 2 days of washout period and on the 6th day in the alternate setting.

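### For outcomes with 20-70% non-detects, ROS fills in individual values without regard to setting, participant or hour, which distorts the setting contrast and the rhythm estimates

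*SAP*

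**What the plan says.** SAP section 3.6 sets three tiers by the share of an outcome's values below the limit of detection (LOD). Below 20%, non-detects become LOD/2. From 20% they are "imputed with regression on order statistics (ROS"), explained as a method in which "non-detect data are replaced based on a probability plot of detects". Above 70% the outcome becomes binary.

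The middle tier names no strata and no covariates. It gives no rule for which void receives which value, no repeated imputation and no censored-data model.

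The completed outcomes feed two analyses:
- the per-subject, per-day and population-mean cosinor fits (section 3.9.1);
- the linear mixed models on setting with participant random intercepts, and the non-linear mixed models of diurnal variation (section 3.9.3).

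On each sampling day the participant "collects the urine voids of the day (at least 4) except for the first morning void", and the next first morning void is added, so there are at least five voids per setting.

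**The concern.** ROS reconstructs the lower tail of one distribution. That is enough for a summary mean or standard deviation. It does not say which non-detect is low and which lies just under the limit.

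The primary analyses are within-person comparisons between settings and across hours, so they depend on which participant, setting and time each value belongs to. If non-detects from both settings draw on one common pool, whatever setting or time-of-day signal remains among them is erased. With up to 70% of values filled in, this could materially understate the setting contrast and the rhythm amplitude. If the filling is done another way, it could produce a difference that does not exist.

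**Working it through.** **Inputs from the SAP.** ROS tier 20-70%, judged per outcome (section 3.6). Five voids per setting (section 2.5). Random-intercept model on setting (section 3.9.3). Natural log scale where outcomes are not normal (section 3.4). Two-sided 95% intervals (section 3.3). Planned size: "the sample size for this two-treatment crossover study was estimated to be 57 subjects" (section 2.9).

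**Planned size reproduced.** It serves only to fix N for the simulation. Within-subject SD of "plasma leptin was assumed to be 3.53 ppb for females and 0.01 ppb for males"; difference of "atleast 1.9 ppb, based on other intervention studies"; "Assuming a power of 80% and a two-sided 5% significance level". With the female SD, the SD of a paired difference is √2 × 3.53 = 4.99. The normal approximation gives (1.960 + 0.842)² × 4.99² / 1.9² = 54.2, so 55. The noncentral t gives 57, as stated.

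**Assumptions, not in the SAP.** Log-normal values and one LOD per outcome. Log-scale between-subject SD 0.3-1.0 and within-subject SD 0.5-0.8. True log differences 0 to 0.6. Non-detect shares of 20, 35, 50 and 70%.

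**Reading 1: one pooled ROS per outcome, values allotted at random.** Let p be the non-detect share, c the standard normal quantile of p, and φ the normal density. Every non-detect has the same expected fill-in, the lower-tail mean μ − σφ(c)/p. Differentiating the expected completed mean of a setting with respect to its true mean gives the share of a small setting difference that survives:

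k(p) = (1 − p) + cφ(c) + φ(c)²/p

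The SDs cancel. Simulated values come from 500 runs per case with 57 subjects, and 800 per case with 55 subjects.

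| p | k(p) | Simulated |
|---|---|---|
| 20% | 0.800 − 0.236 + 0.392 = 0.956 | 0.94-0.97 |
| 35% | 0.650 − 0.143 + 0.392 = 0.899 | 0.89-0.92 |
| 50% | 0.500 + 0 + 0.318 = 0.818 | 0.81-0.84 |
| 70% | 0.300 + 0.182 + 0.173 = 0.655 | 0.64-0.67 |

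A simulated 24-hour amplitude kept 97, 92, 83 and 67%.

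**Source of the coverage loss.** At 70% non-detects and a true log difference of 0.30, the pooled-ROS estimate averaged 0.191 with model SE 0.067 and true sampling SD 0.064. The bias is 0.109, and 0.109/0.067 = 1.63 SE. Coverage expected from bias alone is Φ(1.96 − 1.63) = Φ(0.33), about 63%; the simulation gave 62%. Bias therefore accounts for the loss. With no true difference, false positives stayed near 5%. For true log differences of 0.2 and 0.4 (SDs 0.7 and 0.6), coverage was 91% and 80% at 50% non-detects, and 81% and 50% at 70%.

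**Reading 2: ROS run separately by setting.** The shrinkage disappears (ratio 0.99-1.03). However, all fill-ins in a setting now hang on one fitted line whose error the model ignores. The model SE is 0.65 of the true sampling SD at 50% and 0.42 at 70%. False positives are about 15-19% and 36-40%.

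**Reading 3: sorted ROS values pasted into a file ordered by setting.** With no true effect, a log difference of 0.12, 0.41 and 0.68 appears at 20, 50 and 70% non-detects.

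**Comparator.** Random-intercept censored likelihood on the same simulated data, true log difference 0.30, 120 runs per case:

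| p | Censored: estimate, coverage | Pooled ROS: estimate, coverage |
|---|---|---|
| 20% | 0.304, 96% | 0.291, 94% |
| 50% | 0.305, 98% | 0.251, 84% |
| 70% | 0.292, 97% | 0.191, 62% |

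For a true log difference of 0.2 at 70% non-detects, power was about 78% with censored likelihood and 49% with pooled ROS.

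**The case against.** The rule is prespecified, tiered and referenced, in a study that section 2.1 calls a pilot. The words pooled and once do not appear in section 3.6; both are inferred from a per-outcome rule without strata. The SAP reports no detection rate, so the ROS tier may never be used. Section 2.9's remark that nothing is known about urinary adipokines concerns sample-size inputs and does not show that they fall in this band. At the low end of the tier the loss is small. All of this stands.

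A reader might also infer that filling in values without imputation uncertainty makes the intervals too narrow. Under pooled ROS that is not shown: the model SE is close to the true sampling SD. The ROS intervals are 1, 6 and 14% narrower than the censored-likelihood ones at 20, 50 and 70%, but they surround a shrunken estimate that itself varies less. Standard errors that are much too small arise only when ROS is run by setting.

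A reader might further infer that the plan always biases towards no difference, or always loses a third. The direction depends on implementation, and the third belongs to the 70% limit. Sorted values pasted into a file ordered by participant, for instance, kept 0.92 of a 0.2 log difference at 50% non-detects and 0.79 at 70%.

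What the objection does not remove is that every reading tried goes wrong in the upper part of the tier. Naming the strata or the order of allotment would not be enough.

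**Conclusion.** The concern holds in limited form. Section 3.6 applies a method for summarising a distribution to supply individual outcome values in within-person models.

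On the most natural reading, the setting difference and the diurnal amplitude shrink by about 3-5% at 20% non-detects, 8-11% at 35%, 16-19% at 50% and a third at 70%, and intervals undercover because they are centred in the wrong place. Other readings give inflated false positives or a spurious difference.

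The retained share hardly depends on the assumed SDs. It does rest on log-normality and a single LOD. Coverage and power depend on the assumed SDs and effects as well. Whether any hormone is affected cannot be told from the SAP. The matter is worth settling before analysis, because the plan itself provides for this band.

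**What to change.** For outcomes with 20-70% non-detects, amend sections 3.6 and 3.9 as follows.

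1. Fit the primary setting model by censored maximum likelihood, left-censored at the LOD, with a participant random intercept, setting, 24-hour cosine and sine terms, and the creatinine adjustment already planned in section 3.4. If that adjustment divides by creatinine, the censoring limit must be divided likewise for each void.
2. Estimate the MESOR, amplitude and acrophase for these outcomes from the same censored mixed cosinor model, or from multiple imputation conditional on setting, participant and clock time. Use this in place of ROS-filled values in the cosinor fits of section 3.9.1 and the non-linear models of section 3.9.3.
3. Keep ROS for descriptive summaries or as a sensitivity analysis. If it is kept as the latter, state the strata and how values are allotted.
4. Report the share of non-detects for each outcome and setting.

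The cost is a change of wording and some extra programming, with no change to conduct or data collection. The censored model relies on log-normal residuals, an assumption that log-scale ROS already makes.
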